## CLINICAL STUDY SYNOPSIS

Name of Sponsor: Aprea Therapeutics AB	Name of Monitor: [REDACTED]
Title of the Study: Phase II trial of APR-246 in combination with azacitidine as maintenance therapy for TP53 mutated AML or MDS following allogeneic stem cell transplant	
Protocol Number: A19-11172	
Principal Investigator: [name] (Moffitt Cancer Center, Tampa FL)	
Study Drugs: APR-246 and azacitidine	
Clinical Phase: II	
Objectives:	
Primary Objectives:	

1. To assess relapse-free survival (RFS) in patients with TP53 mutated AML or MDS who receive combination maintenance treatment with APR-246 with azacitidine after undergoing allogeneic hematopoietic stem cell transplant (HSCT).

2. To evaluate the safety and tolerability of APR-246 in combination with azacitidine as maintenance treatment post-HSCT.

	
Secondary Objectives:	

1. To assess the overall survival (OS).

2. To assess non-relapse mortality (NRM).

3. To assess time to progression (TPP).

4. To evaluate cumulative incidence of Grades II-IV and III-IV acute graft versus host disease (GVHD).

5. To evaluate 12-month cumulative incidence of mild, moderate, and severe GVHD.

6. To describe event-free survival (EFS)

	
Exploratory Objectives:	

1. To examine the effect of pre- and post-transplant minimal residual disease (MRD) (TP53 variant allele frequency, VAF) on RFS and overall survival (OS).

	

2. To determine if p53 protein expression and other potential genomic biomarkers at baseline before and after HSCT predicts potential effect on RFS and OS.
3. To determine if *TP53* clonal suppression (serial VAF in bone marrow) after HSCT correlates with outcomes.
4. To evaluate APR-246 plasma pharmacokinetics (PK) when administered with azacitidine after transplantation.
5. To evaluate post-transplant donor engraftment via chimerism studies in blood and bone marrow.

**Endpoints:**

**Primary Endpoints:**

1. RFS
2. Incidence, severity, relatedness of adverse events (AEs) and/or laboratory abnormalities

**Secondary Endpoints:**

1. OS
2. NRM
3. Time to progression or relapse
4. Incidence and grade of acute and chronic GVHD (cumulative)
5. Incidence and grade of acute and chronic GVHD (1-year)
6. EFS

**Exploratory Endpoints:**

1. MRD defined by *TP53* VAF
2. RFS and OS in relation to baseline p53 protein expression (IHC) and other potential genomic biomarkers
3. RFS and OS in relation to clonal suppression, i.e., depth and duration of *TP53* VAF reduction in bone marrow samples repeated every 3 months
4. PK parameters:  $C_{max}$ ,  $AUC_{0-inf}$ ,  $T_{1/2}$
5. Post-transplant donor engraftment via chimerism studies in blood and bone marrow (whole marrow and CD3/CD33 fractions)

**Study Design:**

This is a multi-center, open label, Phase II clinical trial to assess the safety and efficacy of APR-246 in combination with azacitidine as maintenance therapy after allogeneic HSCT for patients with *TP53* mutant AML or MDS.

To be eligible to participate in this study, all patients must have either: 1) pre-screening next generation sequencing (NGS) on peripheral blood (PB) or bone marrow (BM) samples at time of HSCT work up to determine presence of *TP53* mutation status or, 2) previously documented evidence of *TP53* mutation by NGS on PB or BM samples.

[figure not shown]
Patients will sign consent and be prescreened for *TP53* mutant AML or MDS before they have a HSCT (Day 0). During the post-HSCT period (Day 1 to 100 post-HSCT), patients are screened for eligibility to receive APR-246 and azacitidine maintenance treatment. In order to proceed with APR-246 and azacitidine treatment, neutrophil and platelet engraftment (recovery) must be confirmed between Day 30 to Day 100 post-HSCT. APR-246 and azacitidine must be initiated no more than 28 days after confirmation.

APR-246 will be administered on Days 1-4, with azacitidine on Days 1-5, of every 28-day cycle. Patients may receive a maximum of 12 cycles of treatment. Patients may continue to receive study treatment in the setting of relapse or progression, up to a maximum of 12 cycles, provided they are continuing to derive benefit in the opinion of the Investigator.

[figure not shown]
A safety evaluation will be performed by the Safety Monitoring Committee after the first 6 patients have completed 1 cycle of APR-246 and azacitidine combination therapy. The Committee will decide if it is appropriate to continue at the current dose; or, in the event the combination is not tolerated the dose of APR-246 will be reduced for subsequent patients.

### **Trial Overview:**

#### **Prescreening (prior to APR-246 and azacitidine)**

## APR-246 and Azacitidine Treatment Period, EOT and LTFU

### Dose Modification:

	APR-246	Azacitidine
Starting dose level	3.7g 4h infusion days 1-4 q28d cycle	36 mg/m  sc or iv, days 1-5 q28d cycle
-1 dose level reduction	3.3g 4h infusion days 1-4 q28d cycle	36 mg/m  sc or iv, days 1-5 q28d cycle
-2 dose level reduction	3.0g 4h infusion days 1-4 q28d cycle	36 mg/m  sc or iv, days 1-5 q28d cycle

**Number of patients:** At least 31 patients

### Inclusion Criteria:

#### Pre-Screening:

These observations will be done  $\leq$  28 days prior to beginning conditioning chemotherapy in anticipation for allograft infusion.

1. Documentation of a *TP53* gene mutation (which is not benign or likely benign) by NGS based on local evaluation with study eligibility confirmed centrally.
2. Must provide a pre-HSCT bone marrow biopsy.
3. Age  $\geq$ 18 years at the time of signing the informed consent form
4. Institutional Review Board/Independent Ethics Committee (IRB/IEC) approved written informed consent and privacy language as per national regulations (e.g., Health Insurance Portability and Accountability Act Authorization (HIPAA) for US sites) obtained from the participant or legally authorized representative prior to any study-related procedures (including withdrawal of prohibited medication, if applicable).
5. Patient has confirmed, morphologically documented MDS or AML by WHO criteria.
6. Patient is considered a suitable candidate for HSCT and has an acceptable source of allogeneic donor hematopoietic stem cells, as defined per

institutional practice (allogeneic HSCT for any donor source [matched sibling, unrelated donor (URD), mismatched URD, related haploidentical,] and any graft source [BM, PB], and any non-study conditioning [myeloablative conditioning (MAC), reduced intensity conditioning (RIC), or non-myeloablative conditioning (NMA)] will be permitted). Additionally, any standard (non-study) GVHD prophylaxis regimen will be permitted.

7. Females must either:
  - a. Be of non-childbearing potential
    - i. postmenopausal (defined as at least 1 year without menses) prior to screening, or
    - ii. documented as surgically sterilized at least 1 month prior to the screening visit
  - b. Or, if of childbearing potential,
    - i. Agree not to try to become pregnant during the study and for 6 months after the final study drug administration
    - ii. And have a negative serum pregnancy test at screening
    - iii. And, if heterosexually active, agree to consistently use highly effective contraception per locally accepted standards in addition to a barrier method starting at screening and throughout the study period and for 6 months after final study drug administration.
8. Females must agree not to breastfeed or donate ova throughout the study drug treatment period and for 6 months after the final study drug administration.
9. Males (even if surgically sterilized), and their partners who are women of childbearing potential must be using highly effective contraception in addition to a barrier method throughout the study drug treatment period and for 127 days after the final study drug administration.
10. Males must not donate sperm throughout the study drug treatment period and for 127 days after the final study drug administration.

**Exclusion Criteria Pre-Transplant:**

1. Patient has had a prior allogeneic transplant.
2. Patient has any of the following cardiac abnormalities (as determined by treating physician):
  - a. Myocardial infarct within six months prior to registration
  - b. New York Heart Association Class III or IV heart failure or known left ventricular ejection fraction (LVEF) < 40%
  - c. A history of familial long QT syndrome

- d. Symptomatic atrial or ventricular arrhythmias not controlled by medications
- e. QTc  $\geq$  470 ms calculated from a mean of 3 ECG readings using Fridericia's correction (QTcF = QT/RR0.33). Patients with QTc  $\geq$  470 ms and bundle branch block and/or pacemaker rhythm may be enrolled following approval by the Medical Monitor.

**Post-transplant Inclusion Criteria for APR-246 and azacitidine treatment:**

1. Patient has received one allogeneic transplant for AML or MDS. At time of treatment, patient must be in morphologic remission for AML or MDS as defined as < 5% blasts for AML and  $\leq$  5% blasts for MDS, and in cytogenetic remission with no morphologic characteristics of acute leukemia (e.g., Auer Rods) in the BM with no evidence of extramedullary disease such as central nervous system involvement or granulocytic sarcoma. Patients with CR with incomplete count recovery (CRp or CRi) are allowed. Incomplete platelet recovery (CRp) is defined as CR with platelet count  $< 100 \times 10^9/L$ . Incomplete blood count recovery (CRi) is defined as CR with neutropenia  $< 1 \times 10^9/L$  with or without complete platelet recovery. Red blood cell count (RBC) and platelet transfusion independence is not required.
2. Any standard (non-study) conditioning [MAC, RIC, or NMA] will be permitted. Acceptable source of allogeneic donor hematopoietic stem cells, as defined per institutional practice (allogeneic HCT for any donor source [matched sibling, URD, mismatched URD, or related haploidentical] and any PB or BM graft source.
3. Patient is  $\geq$  30 days and  $\leq$  100 days from hematopoietic cell infusion.
4. Patient is in complete remission after the transplant and has achieved engraftment. Engraftment is defined as ANC  $\geq 500/\mu L$  and platelets  $\geq 20000/\mu L$  on 3 consecutive measurements (each occurring at least 1 day apart). The patient must not have had a platelet transfusion within 7 days prior to the first measurement.
5. Patients who have developed grades II-IV acute GVHD will be allowed to initiate maintenance therapy based on the following criteria:
  - Does not require high dose steroids as defined as dosage of  $> 0.5 \text{ mg/kg}$  of prednisone (or equivalent) daily dose within 1 week of post-HSCT screening
  - No escalation of systemic immunosuppression in terms of increase of corticosteroids or addition of new agent/modality within 2 weeks of post-HSCT screening. Dose adjustments (both increase and decrease) of GVHD preventative medications such as calcineurin inhibitors or sirolimus to achieve therapeutic trough levels, is allowed. Topical skin and topical gastrointestinal steroids are allowed.

6. Females must either:
  - Be of non-childbearing potential
    - postmenopausal (defined as at least 1 year without menses) prior to screening, or
    - documented as surgically sterilized (e.g., hysterectomy or tubal ligation) at least 1 month prior to the screening visit
  - Or, if of childbearing potential,
    - Agree not to try to become pregnant during the study and for 6 months after the final study drug administration
    - And have a negative serum pregnancy test at screening
    - And, if heterosexually active, agree to consistently use highly effective contraception per locally accepted standards in addition to a barrier method starting at screening and throughout the study period and for 6 months after final study drug administration.
7. Females must agree not to breastfeed or donate ova throughout the study drug treatment period and for 6 months after the final study drug administration.
8. Males (even if surgically sterilized), and their partners who are women of childbearing potential must be using highly effective contraception in addition to a barrier method throughout the study drug treatment period.
9. Males must not donate sperm throughout the study drug treatment period.
10. Agrees not to participate in another interventional study while on treatment.
11. Karnofsky Performance Status 70 or greater is required.
12. Patient has adequate organ function as defined by the following laboratory values:
  - a. Creatinine clearance > 30 mL/min by Cockcroft-Gault formula;
  - b. Total serum bilirubin < 1.5 x ULN unless due to Gilbert's Syndrome, underlying disease of MDS, hemolysis or considered an effect of regular blood transfusions;
  - c. ALT/AST < 2.5 x ULN, unless due to underlying disease of MDS.

**Post-transplant Exclusion Criteria for APR-246 and azacitidine treatment:**

1. Use of umbilical cord blood donor and stem cell source.
2. Patient has uncontrolled infection. Definitive therapy for infection is required and must have no signs of progression within 7 days of first day of study drug treatment.
3. Use of investigational agent within 14 days of pre-HSCT screening or

anytime thereafter.

4. Use of hypomethylating agent, cytotoxic chemotherapeutic agents, or experimental agents (agents that are not commercially available) for the treatment of MDS or AML within 14 days of the first day of pre-HSCT screening or anytime thereafter.
5. Patient has used experimental therapy for acute GVHD at any time post-transplant. If unsure of the definition of "experimental", discussion with the Medical Monitor is recommended.
6. Patient requires treatment with supplemental oxygen not including usage of non-invasive CPAP at night.
7. Patient has any of the following cardiac abnormalities (as determined by treating physician):
  - a. Myocardial infarct within six months prior to registration
  - b. New York Heart Association Class III or IV heart failure or known LVEF<40%
  - c. A history of familial long QT syndrome
  - d. Symptomatic atrial or ventricular arrhythmias not controlled by medications
  - e. QTc  $\geq$  470 ms calculated from a mean of 3 ECG readings using Fridericia's correction ( $QTcF = QT/RR^{0.33}$ ). Patients with QTc  $\geq$  470 ms and bundle branch block and/or pacemaker rhythm may be enrolled after approval by the Medical Monitor.

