## 4.0 TRIAL DESIGN

### 4.1 Overview of Trial Design

This is a multi-center, open label, Phase II clinical trial to assess the safety and efficacy of APR-246 in combination with azacitidine as maintenance therapy after allogeneic HSCT for patients with *TP53* mutant AML or MDS.

To be eligible to participate in this study, all patients must have either: 1) pre-screening NGS on peripheral blood (PB) or bone marrow (BM) samples at time of HSCT work up to determine presence of *TP53* mutation status or, 2) previously documented evidence of *TP53* mutation by NGS on PB or BM samples.

[figure not shown]
Patients will sign consent and be prescreened for *TP53* mutant AML or MDS before they have a HSCT (Day 0). During the post-HSCT period (Day 1 to 100 post-HSCT), patients are screened for eligibility to receive APR-246 and azacitidine maintenance treatment. In order to proceed with APR-246 and azacitidine treatment, neutrophil and platelet engraftment (recovery) must be confirmed between Day 30 to Day 100 post-HSCT. APR-246 and azacitidine must be initiated no more than 28 days after confirmation.

APR-246 will be administered on Days 1-4, with azacitidine on Days 1-5, of every 28 day cycle. Patients may receive a maximum of 12 cycles of treatment. Patients may continue to receive study treatment in the setting of relapse or progression, up to a maximum of 12 cycles, provided they are continuing to derive benefit in the opinion of the Investigator.

[figure not shown]
A safety evaluation will be performed by the Safety Monitoring Committee after the first 6 patients have completed 1 cycle of APR-246 and azacitidine combination therapy. The Committee will decide if it is appropriate to continue at the current dose; or, in the event the combination is not tolerated (e.g. patients experience dose limiting toxicity) the dose of APR-246 will be reduced for subsequent patients.

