#### **4.8 Registration**

Prior to registration and any study-specific evaluations being performed, all patients must have given written informed consent for the study and must have completed the pre-study evaluations. Patients must meet all eligibility requirements listed in Section 5.0. Patients will be registered on the study by using the [REDACTED] Interactive Web Response System (IWRS) automated patient registration system (see the Study Operations Manual for specific instructions).

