## 5.0 SELECTION AND WITHDRAWAL OF SUBJECTS

To participate in this study, patients must meet:

- Transplant and enrollment criteria in Sections 5.1.1-5.1.2; and,
- APR-246 and azacitidine treatment criteria in Sections 5.2.1-5.2.2.

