#### 7.1.1 Pre-Screening (Day -28 to -1 prior to HSCT)

- Sign informed consent
- *TP53* mutation confirmation
- Disease assessment: BM aspirate and/or biopsy sample must be collected prior to the start of the pre-transplant conditioning regimen.
- Pregnancy test (women of child-bearing potential only)
- ECGs; see Table 7.

#### 7.1.2 Day 0

- Transplant

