#### 7.1.3 Post-Transplant, APR-246 Screening Period (Day 1 to 100)

Post-HSCT evaluation will occur as per institutional standard practices.

APR-246/azacitidine screening period occurs during Day 30 to 100 post-HSCT. The date will vary but should start (Day -28 relative to first dose) as soon as engraftment and the requirements in Section 7.1.4 are confirmed. The first dose must be administered no more than 28 days after confirmation.

The procedures listed below should be performed within 28 days prior to the first dose, or as indicated. Starred (\*) procedures should be done within 3 days prior to the first dose.

- Sign informed consent
- Disease assessment
- Eligibility
- Karnofsky performance status

- Medical history and Transplant Details
- Physical exam with Weight\*
- Vital signs\*
- CBC\*
- CMP\*
- ECGs\*; see Table 7.
- Pregnancy test (women of child-bearing potential only)\*
- Pre-treatment/baseline Bone marrow (BM)/Aspirate (BMA) for correlatives/exploratory: see Table 9
- GVHD monitoring
- Chimerism, immune reconstitution
- Monitor adverse events
- Concomitant medications

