### **7.3 End of Treatment Visit**

Patients discontinuing study early should complete their end of treatment (EOT) visit within 30 days after their last dose. For patients who complete treatment per protocol, EOT is the last day of APR-246 and azacitidine dosing in Cycle 12.

If patients discontinue prior to receiving any APR-246 or azacitidine, the EOT is the date of relapse or Day 100 post-HSCT (the last day of post-transplant window eligibility requirement).

The following should be performed at EOT:

- Disease assessment (blood and bone marrow)
- Vital signs
- CBC
- CMP
- ECGs; see Table 7.
- Pregnancy test (women of child-bearing potential only)
- Adverse events
- Concomitant medications

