#### **8.1.3 Reporting of Adverse Events**

##### **8.1.3.1 Adverse Events**

An adverse event (AE) is any untoward medical occurrence in a patient or clinical investigation subject administered a pharmaceutical product that does not necessarily have a causal relationship with the treatment. An adverse event can be any unfavorable and unintended sign (including a laboratory finding), symptom or disease temporally associated with the use of a medicinal (investigational) product, whether or not related to the medicinal (investigational) product.

The AE reporting period starts from the day of signing consent. If an AE occurs before the first dose of study drug it will be considered a non-treatment emergent AE. All AEs will be collected for 30 days after the last dose of study drug; see Section 8.1.4 for GVHD reporting.

At each evaluation patients should be interviewed in a non-directed manner to elicit potential adverse reactions from the patient. The occurrence of an adverse event will be based on changes in the patient's physical examination, laboratory results, and/or signs and symptoms.

All adverse events (except grade 1 and 2 laboratory abnormalities that do not require an intervention), regardless of causal relationship, are to be recorded in the case report form and source documentation. The Investigator must determine the intensity of any adverse events according to the NCI Common Terminology Criteria for Adverse Events (CTCAE) Version 5.0 (see [https://ctep.cancer.gov/protocoldevelopment/electronic\\_applications/ctc.htm#ctc\\_50](https://ctep.cancer.gov/protocoldevelopment/electronic_applications/ctc.htm#ctc_50)) and their causal relationship. Those AEs not covered by these criteria will be graded as follows:

1. Mild: Discomfort noticed, but no disruption of normal daily activity. Prescription drug not ordinarily needed for relief of symptom but may be given because of personality of patient.
2. Moderate: Discomfort sufficient to reduce or affect normal daily activity. Patient is able to continue in study; treatment for symptom may be needed.
3. Severe: Incapacitating, severe discomfort with inability to work or to perform normal daily activity. Severity may cause cessation of treatment with test drug; treatment for symptom may be given and/or patient hospitalized.

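### Post-transplant exclusion 7a counts its six-month infarct look-back from registration rather than first dose, so an infarct between the two is not excluded

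*Combined protocol and SAP*

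**What the plan says.** Item 7a of the post-transplant exclusions, in the synopsis and in 5.2.2, reads "Myocardial infarct within six months prior to registration". The pre-transplant exclusion 2a, in the synopsis and 5.1.2, is identical.

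Section 4.8 does not date registration. It requires consent and completed pre-study evaluations first, and adds: "Patients must meet all eligibility requirements listed in Section 5.0". Section 5.0 contains both the pre-transplant criteria (5.1) and the post-transplant criteria (5.2), and describes the former as "Transplant and enrollment criteria in Sections 5.1.1-5.1.2". Section 7.3 provides for patients who are never dosed: "If patients discontinue prior to receiving any APR-246 or azacitidine, the EOT is the date of relapse or Day 100 post-HSCT".

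The windows that matter are these:
- 7.1.1 is headed "Pre-Screening (Day -28 to -1 prior to HSCT"; 5.1.1 instead counts its 28 days back from the start of conditioning.
- Section 4.1 places engraftment confirmation on Day 30 to Day 100 and says "APR-246 and azacitidine must be initiated no more than 28 days after confirmation".
- Inclusion 3 in 5.2.1 requires the patient to be 30 to 100 days from cell infusion.

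**The concern.** Item 7a decides whether a patient may receive study drug, but its look-back ends at registration. An infarct five months before registration excludes the patient; one a week before first dose, if it came after registration, does not. The rule therefore misses the most recent infarcts.

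Neighbouring criteria are not built this way. In the same list, item 2 (infection) is tied to the first day of study drug, and items 3 and 4 run on from pre-HSCT screening without an end date. Within item 7, sub-items 7b, 7d and 7e mainly describe the patient's present condition. Item 7a alone has a look-back that stops at registration, which suggests it was carried over from 2a without a new anchor.

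What is at stake is patient safety and uniform eligibility across the sites of a multi-center trial. No efficacy figure depends on it.

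**Working it through.** The documents give no figure for this gap, so there is nothing to reproduce first. The check is calendar arithmetic in days relative to transplant (Day 0):

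uncovered interval = first-dose day − registration day.

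**Inputs**
- Pre-transplant window: Day -28 to Day -1 (7.1.1).
- Confirmation: Day 30 to Day 100 (4.1).
- Confirmation to first dose: 0 to 28 days (4.1).
- Earliest first dose: Day 30. Latest: 100 + 28 = Day 128, or Day 100 if inclusion 3 is applied on the dosing day.
- Six months taken as 183 days.
- c = days from start of conditioning to transplant. The documents do not give it; 4 to 10 is assumed.

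**Reading A: registration before transplant**

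Support: 5.0 calls the 5.1 list enrollment criteria, 7.3 defines an end of treatment for patients never dosed, and 2a uses registration as a pre-transplant anchor.

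| Case | Calculation | Days |
|---|---|---|
| Shortest | 30 − (−1) | 31 |
| Longest | 128 − (−28) | 156 |
| Longest, first dose by Day 100 | 100 − (−28) | 128 |
| Longest, pre-screening counted from conditioning | 128 + 28 + c = 156 + c | 160 (c = 4), 163 (c = 7), 166 (c = 10) |

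On this reading 7a adds nothing to 2a, because both look back from the same date.

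**Reading B: registration after all Section 5.0 criteria are met**

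Support: the literal text of 4.8.

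The gap runs only from clearance to first dose: 0 to 28 days. The look-back does cover transplant:
- From registration on Day 30 it reaches 30 − 183 = Day -153.
- From registration on Day 100 it reaches 100 − 183 = Day -83.

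On this reading 2a, applied at pre-screening, counts back from a date that has not yet occurred. Each reading therefore leaves one of the two items not working as intended.

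**Would another rule close the gap?**

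Consider a patient with a recent infarct, LVEF of 40% or more, NYHA class I or II, controlled rhythm, QTc below 470 ms, no oxygen requirement and Karnofsky 70. That patient passes 7b, 7d, 7e, exclusion 6 and inclusion 11. Starred screening items in 7.1.3 ("procedures should be done within 3 days prior to the first dose") include exam, vital signs, CMP and ECG, and a further ECG precedes the first dose on Cycle 1 Day 1. These may reveal an infarct, but no stated rule then excludes the patient for it. Only clinical judgment remains.

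**Check of the proposed anchor**

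Counting 183 days back from the latest first dose gives 128 − 183 = Day -55. That is 27 days before Day -28, and 20 days before Day -35 (28 days before conditioning at c = 7). It covers any c up to 27, and the interval left uncovered falls to 0 days on both readings.

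**The case against.** The strongest reply is that the long interval rests on the reading with less support in the section that governs registration. Section 4.8 requires all of Section 5.0, which includes the post-transplant criteria, so registration would follow clearance and the gap would be at most 28 days. Section 7.1.3 lists a second consent in the APR-246 screening period, which also suggests a later entry step. Calling the 5.1 list enrollment criteria does not date registration, and an end-of-treatment date for undosed patients needs only that consented patients are tracked. Section 4.8 also refers to the Study Operations Manual; if sites register at Cycle 1 Day 1, the gap is close to zero. Item 7 is left to the treating physician's determination, and intercurrent illness or investigator discretion (5.3) can stop therapy. Finally, the missing registration date matters more for RFS, OS and EFS, which all start there.

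Much of this stands. The 31 to 156 days are possible but not established, the documents give no infarct rate, and the practical risk is small. But the physician's judgment concerns whether the abnormality is present and does not move the date in 7a. The other checks are not infarct exclusions. On the literal reading the gap shrinks without disappearing, and 2a then has the wrong anchor instead. That registration timing matters elsewhere is a further reason to state it.

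**Conclusion.** The concern holds. As worded, 7a does not exclude an infarct between registration and first dose. The interval is 0 to 28 days if registration follows post-transplant clearance, and 31 to 156 days if it precedes transplant (at most 128 if first dose must fall by Day 100, or 160 to 166 if pre-screening is counted from conditioning with an assumed c of 4 to 10 days). The literal text of 4.8 favours the short interval; the documents do not settle the matter.

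This is a wrong anchor in a stated rule. It should be corrected, but its weight is modest: few of the roughly 31 patients are likely to be affected, other checks would catch some of them, and power, alpha and sample size are unchanged. Confidence is medium because the timing of registration is not given. The six-month length itself is not in question.

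**What to change.** 1. In the synopsis and 5.2.2, count the six months in 7a back from the first dose of study drug.
2. In the synopsis and 5.1.2, count the six months in 2a back from pre-HSCT screening.
3. In 4.8, add one sentence stating when registration occurs.

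The cost is wording only. The information is already collected: medical history within 28 days and ECG within 3 days before first dose, and for adverse events, "The AE reporting period starts from the day of signing consent". The one downside is that at most a few patients with a recent infarct become ineligible, which is the evident purpose of the criterion.
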